6.9.1 Prior Medications

A medication history will be taken at Screening. All medications taken within 1 week before Day 0 will be entered into the eCRF.

6.9.2 Concomitant Medication

All concomitant medications taken during the study will be recorded in the patient's eCRF.

6.10 Prohibited Medications

The following medications are prohibited:

- Local biologicals
- Cyclophosphamide or chlorambucil
- Immunosuppressive, immunomodulatory or steroid treatment for any other disease than uveitis
- Any anticoagulant or thrombocyte aggregation inhibiting agent (marcumar, warfarin, heparin, enoxaparin, apixaban, rivaroxaban, pentosanpolysulfate, dabigatran, aspirin and others)
- Any systemic antibiotic treatment

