6.1 Surgical Procedure

The study treatment procedure must be performed only by the qualified Investigator in an operating room, surgical suite, or in an office setting using sterile technique. The study medication kit should be readily available during the procedure. The final diluted PP-001 solution will be injected at the required dose at a volume of 100 μ L (see Section 8). For safety reasons, an emergency pars plana vitrectomy aiming at removal of injected drug will be available in case of a severe adverse event including, but limited to, acute loss of visual acuity or acute inflammatory or toxic response to injection. It is therefore mandatory for patients to remain in the hospital for at least 4 hours after the injection procedure.

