4.2 Analysis sets

4.2.1 Per-Protocol Analysis Set

The PP set will include all Safety Set patients who have no major protocol deviations, and who complete the study up to the end of the post-study assessments (including telephone call days).

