5.6 Prior and concomitant medications

Definitions and data conventions

The following categories of medications will be identified:

- previous medication (stop date \leq date of first study medication intake);
- concomitant medication (stop date $>$ date of first study medication intake or stop date ongoing/missing).

In case of missing or incomplete dates/times not directly allowing allocation to any of the two categories of medications, a worst-case allocation will be done according to the available parts of the start and the end dates. The medication will be allocated to the first category allowed by the available data, according to the following order:

- concomitant medication;
- previous medication.

Statistical analysis

Previous and Concomitant medications

Medications will be coded using WHO Drug Dictionary (WHO-DD), version 2016Q1 (1st Quarter of 2016), and the following Anatomical Therapeutic Chemical Classification (ATC) codes:

- Anatomical Main Group (ATC 1st level code);
- Chemical subgroup (ATC 4th level code);
- Preferred name.

Previous and concomitant medications will be summarized separately for Safety set by anatomical main group, chemical subgroup and preferred name by cohort.

Subjects experiencing more than one previous (or concomitant) medication within the same anatomical main group, chemical subgroup and preferred name will be counted only once.

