8.1 Adverse events

Definitions and data conventions

Pre-treatment adverse events

An AE will be classified as pre-treatment AE if it starts before the date/time of first study medication intake (AE onset date/time < date/time of first study medication intake).

Treatment-emergent adverse event (TEAE)

An AE will be classified as a TEAE if it starts on or after the date/time of first study medication intake (AE onset date/time \geq date/time of first study medication intake).

In case of missing or incomplete dates/times not allowing a direct allocation to any of the two categories of AEs, a worst-case allocation will be done according to the available parts of the onset and the end dates/times. The AE will be allocated to the first category allowed by the available data, according to the following order:

- TEAE
- Pre-treatment.

Serious adverse event (SAE)

A SAE is an AE judged as serious.

Adverse drug reaction (ADR)

An ADR is an AE judged as “Possibly Related”, “Probably Related” or “Definitely Related”.

Adverse event leading to discontinuation

An AE leading to discontinuation is an AE with action taken equal to “Study drug withdrawn and /or patient withdrawn from the study”.

Adverse event leading to death

An AE leading to death is an AE with outcome equal to “Fatal”.

| Forms | | | |
|--------------|--|------------------------------------|----------------|
| Title | | Statistical Analysis Plan Template | |
| Code | | Version | Effective Date |
| FRM_ST03_032 | | 01 | 23 Apr 2015 |
| | | 27 of 31 | |

Count of adverse events

Two AEs with the same Preferred Term (PT) and classified in the same category (pre-treatment AE or TEAE) will be considered as two different events when calculating the “number of events” in the tables.

Statistical analysis

Pre-treatment AEs and TEAEs will be presented separately. Pre-treatment AEs will be presented in the listings only.

The number of treatment-emergent AEs, SAEs, ADRs, serious ADRs, severe AEs, AEs leading to discontinuation and AEs leading to death, and the number and the percentage of patients experiencing treatment-emergent AEs, SAEs, ADRs, serious ADRs, severe AEs, AEs leading to discontinuation and AEs leading to death will be summarised by cohort.

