9.3 Tables

The list of tables is provided here below:

| TABLE | TITLE |
|----------------|---|
| TABLE 14.1.1 | SUBJECT DISPOSITION / SUMMARY OF ALL SUBJECTS |
| TABLE 14.1.2.1 | PRIMARY REASONS FOR DISCONTINUATION FROM STUDY / SAFETY SET |
| TABLE 14.1.3.1 | ANALYSIS SETS / SAFETY SET |
| TABLE 14.1.4.1 | DEMOGRAPHIC CHARACTERISTICS / SAFETY SET |
| TABLE 14.1.5.1 | MEDICAL AND OPHTHALMIC HISTORY: PAST DISEASES / SAFETY SET |
| TABLE 14.1.5.2 | MEDICAL AND OPHTHALMIC HISTORY: CONCOMITANT DISEASES // SAFETY SET |
| TABLE 14.1.6.1 | PREVIOUS MEDICATIONS / SAFETY SET |
| TABLE 14.1.6.2 | CONCOMITANT MEDICATIONS / SAFETY SET |
| TABLE 14.2.2.1 | ETDRS SCORES DURING THE STUDY AND CHANGE FROM BASELINE / SAFETY SET |
| TABLE 14.2.2.2 | ETDRS SCORES DURING THE STUDY AND CHANGE FROM BASELINE / PP SET |

| Forms | | | | |
|--------------|--|------------------------------------|----------------|----------|
| Title | | Statistical Analysis Plan Template | | |
| Code | | Version | Effective Date | Page |
| FRM_ST03_032 | | 01 | 23 Apr 2015 | 30 of 31 |

| TABLE | TITLE |
|----------------|---|
| TABLE 14.2.3.1 | SLIT LAMP EXAMINATION DURING STUDY / SAFETY SET |
| TABLE 14.2.4.1 | FLUORESCEIN ANGIOGRAM, ETDRS, VISUALLY EVOKED CORTICAL POTENTIAL, INTRAOCCULAR PRESSURE AND DILATED FUNDOSCOPY DURING STUDY / SAFETY SET |
| TABLE 14.2.5.1 | ELECTRORETINOGRAPHY, OPTICAL COHERENCE TOMOGRAPHY, VISUAL FIELD, CORNEAL ENDOTHELIAL MICROSCOPY, FUNDUS PHOTOGRAPHY AND AMSLER GRID DURING STUDY / SAFETY SET |
| TABLE 14.2.6 | PATIENT- REPORTED OUTCOMES DURING THE STUDY AND CHANGE FROM BASELINE / SAFETY SET |
| TABLE 14.3.1.1 | SUMMARY OF TREATMENT EMERGENT ADVERSE EVENTS / SAFETY SET |
| TABLE 14.3.1.2 | TREATMENT EMERGENT ADVERSE EVENTS BY SYSTEM ORGAN CLASS AND PREFERRED TERM / SAFETY SET |
| TABLE 14.3.1.3 | TREATMENT EMERGENT SERIOUS ADVERSE EVENTS BY SYSTEM ORGAN CLASS AND PREFERRED TERM / SAFETY SET |
| TABLE 14.3.1.4 | TREATMENT EMERGENT ADVERSE DRUG REACTIONS BY SYSTEM ORGAN CLASS AND PREFERRED TERM / SAFETY SET |
| TABLE 14.3.1.5 | TREATMENT EMERGENT ADVERSE EVENTS LEADING TO DISCONTINUATION BY SYSTEM ORGAN CLASS AND PREFERRED TERM / SAFETY SET |
| TABLE 14.3.1.6 | TREATMENT EMERGENT ADVERSE EVENTS LEADING TO DEATH BY SYSTEM ORGAN CLASS AND PREFERRED TERM / SAFETY SET |
| TABLE 14.3.2.1 | HAEMATOLOGY RESULTS DURING THE STUDY AND CHANGE FROM SCREENING / SAFETY SET |
| TABLE 14.3.2.2 | BIOCHEMISTRY RESULTS DURING THE STUDY AND CHANGE FROM SCREENING / SAFETY SET |

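### New uveitis treatment after the injection is largely permitted, but SAP 5.6 sorts drugs by stop date, so the concomitant-medication table as described cannot separate it from continued background therapy

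*Protocol*

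**What the plan says.** **What may be given after the injection.** Protocol 6.10 bars local biologicals, cyclophosphamide and chlorambucil whatever the reason. For the wider class the bar depends on indication: "Immunosuppressive, immunomodulatory or steroid treatment for any other disease than uveitis". Inclusion criterion 9 asks that systemic therapy present at study start be continued. Exclusion criteria 4 to 6 on intravitreal injections, periocular steroid and steroid implants look back from Baseline or Day 0.

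**How drugs are classified.** SAP 5.6 has two categories. The first is "previous medication (stop date" on or before the date of first study drug. The second is a stop date after the "date of first study medication intake or stop date ongoing/missing". Start dates are used only when dates are missing or incomplete, and the result is still one of the same two categories. SAP 5.3 sets the date of first intake as the Day 0 injection date. SAP 8.1, by contrast, works to date and time for adverse events: "An AE will be classified as a TEAE if it starts on or after the date/time of first study medication intake".

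**What is shown.** SAP 9.3 lists Table 14.1.6.2 as "CONCOMITANT MEDICATIONS / SAFETY SET". SAP 5.6 describes it by ATC level, preferred name and cohort, without timing. SAP 3.5.1 and 7.1 name ETDRS change at Day 14 and Day 28 as the primary efficacy variable. SAP 7.1 and 7.2 summarise observed values by visit and cohort.

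**The concern.** The secondary objective is improvement of inflammation after PP-001, in cohorts of four with no control group. If a study eye flares and the investigator adds systemic or periocular steroid, the later ETDRS, vitreous haze and OCT values reflect both treatments. Treating the flare is right, and summarising all observed values is a legitimate choice. But a reader of the Day 14 and Day 28 summaries needs to know how many patients in each cohort were in that position. The medication table is where one would look, and its classification rule discards the item needed, which is whether the drug began before or after the injection.

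A second effect arises on Day 0 itself. Protocol 6.1 provides for emergency vitrectomy in case of "acute inflammatory or toxic response to injection", so drug treatment of an acute reaction on that day is foreseeable. A single dose given then would appear in the table of previous medications.

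**Working it through.** The plan states no figure on this point, so there is nothing to reproduce. The check has three parts.

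**1. Is new uveitis treatment prohibited anywhere in the supplied protocol?** Section 6.10 makes the class-wide bar depend on the disease treated, and uveitis is the exempt one. Inclusion 9 may suggest that stable background therapy was intended, but it forbids neither a new drug nor a higher dose. Exclusions 4 to 6 apply before entry. So the answer is no, apart from the three items barred outright.

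**2. SAP 5.6 applied to made-up records with complete dates.** Rule: *previous* if stop date ≤ Day 0; otherwise *concomitant*.

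| Record | Start | Stop | SAP 5.6 class |
|---|---|---|---|
| Background steroid | Day −200 | ongoing | concomitant |
| Background steroid, stopped early | Day −200 | Day 10 | concomitant |
| New systemic steroid | Day 5 | ongoing | concomitant |
| New single periocular steroid | Day 12 | Day 12 | concomitant |
| Single dose the day after injection | Day 1 | Day 1 | concomitant |
| Drug ended on injection day | Day −30 | Day 0 | previous |
| Single dose after injection, same day | Day 0 | Day 0 | previous |

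The first two rows are background therapy and the next three are new treatment; all five share one class. The last row is treatment given after PP-001 but classed as given before it. The same drug one day later would be *concomitant*. The worst-case allocation in SAP 5.6 does not help, because it applies only to missing or incomplete dates.

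**3. How far can one patient move a cohort summary?** Shift in mean = gain ÷ n. The letter gains are assumptions.

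| Assumed gain (letters) | n = 4 | n = 6 (two patients added under SAP 3.1) |
|---|---|---|
| 5 | 5/4 = 1.25 | 5/6 = 0.83 |
| 10 | 10/4 = 2.5 | 10/6 = 1.67 |
| 15 | 15/4 = 3.75 | 15/6 = 2.5 |

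The median may not move. With the other three patients at 0 and the fourth going from 0 to +10, the mean goes from 0 to 2.5 and the median stays at 0.

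Dropping the affected values would not be neutral either. Take the other three at −5, 0 and +5. If the fourth would be at −5 untreated, the mean is −5/4 = −1.25. If the fourth reaches +5 after added steroid, the mean is 5/4 = +1.25. Excluding the fourth gives 0/3 = 0, still 1.25 above the untreated mean.

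**The case against.** The strongest reply is that this is table layout in a first-in-human study of 12 planned patients with no efficacy inference. SAP 4.1 commits to listing all endpoint data collected, and Listing 16.2.4.3 holds the medications. Counting the cases needs only that listing and the visit dates. This stands, and it limits the point to a cheap improvement. It does not answer the misclassification: a written rule puts some treatment given after the injection under *previous*, and a better rule costs almost nothing.

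A flare that prompts treatment may also appear as an adverse event, since Protocol 7 requires new or worsened occurrences to be reported. That route is partial. The same section exempts some disease-related findings, and the adverse event tables do not show when treatment began.

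The per-protocol set might be expected to remove these patients: "The PP set will include all Safety Set patients who have no major protocol deviations". It need not. Treatment that 6.10 allows is not a deviation from 6.10, violations are judged case by case (SAP 5.2), and vitreous haze and OCT are summarised on the Safety set only.

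A reader might infer several stronger things that the documents do not support:

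- *That treated patients would be counted as PP-001 responders.* The SAP defines no improved category for ETDRS, haze or OCT.
- *That the plan should ban such treatment or exclude later values.* Freedom to treat is appropriate, and the arithmetic above shows that exclusion favours the drug in its own way.
- *That every national protocol permits it.* Only one version is supplied; it has the Day 21 visit that the SAP assigns to Austria and Germany.

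**Conclusion.** The point holds, with a narrow effect. In the supplied protocol version, most steroid and immunosuppressive treatment for uveitis may be started after the injection. For complete dates, the SAP's stop-date rule prevents Table 14.1.6.2 as described from separating it from background therapy, and drugs given and stopped on Day 0 after the injection are placed under *previous*.

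What is affected is the reading of the Day 14 and Day 28 efficacy summaries. Since efficacy is descriptive, no error rate is involved, and neither safety conclusions nor dose escalation depend on this table. How often added treatment would occur is not stated in the documents, and no rate is assumed here; the letter shifts show only what one patient could do. ETDRS values at Day 2 and Day 7 are also tabulated and may precede any added treatment, but they are not the named time points. The table shells are in a separate appendix that was not available, so the conclusion rests on the tables as the SAP text describes them.

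**What to change.** All planned summaries stay.

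1. **SAP 5.6 and Table 14.1.6.2.** Split concomitant medications by start date into ongoing at injection, started on Day 0, and started after Day 0. Move drugs started on Day 0 out of *previous* unless a recorded time shows that they ended before the injection.
2. **A count beside the efficacy summaries.** For each cohort, report the number of patients who, after the injection and on or before the Day 14 and Day 28 visits, started a new systemic, periocular or intravitreal corticosteroid or immunosuppressant for uveitis or for an ocular inflammatory adverse event. Identify them by drug name, indication and start date, and by route and eye if the eCRF holds these. This is 3 cohorts × 2 visits = 6 counts. Flag the patients in the efficacy listings.
3. **A note on limits.** State that dose increases may not be captured, because Protocol 6.9 does not list dose among its minimum items. State the same for topical steroid not given for an adverse event, because 6.9 does not record it.

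The cost is a change of SAP wording, a few extra table rows and a listing flag. Drug name, indication and start and stop dates are already required by Protocol 6.9. Route and treated eye are not in that minimum, so the eCRF should be checked before the count is made to depend on them.

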6.11 Non-Pharmacologic Treatments and Procedures

Non-pharmacologic treatments and procedures (e.g., diagnostic) that occur during the study will be entered into the eCRF, including the date and reason for the treatment/procedure.

6.12 Sample Collection for Pharmacokinetic Analysis

6.12.1 Plasma Sample Collection

Blood samples for pharmacokinetic analysis of PP-001 in plasma following intraocular dosing will be collected at Screening, 4 h \pm 1 h after dosing and on Day 2.

Blood samples will be collected from a vein in the opposite arm from the arm in which infusion is given into tubes containing K₃EDTA, as a coating, and immediately chilled on crushed ice. Plasma will be separated by centrifugation at approximately 2,000g for approximately 10 minutes at approximately +4 °C and transferred in equal aliquots (at least 300 µl) to 3 polypropylene screw top cryo vials labeled with the following: PP-001-1001, subject number,

date of dosing, nominal sampling time, aliquot ID (e.g. A, B, C). Promptly following centrifugation, plasma specimens will be immediately frozen and stored at approximately -20 °C or cooler until transported for analysis. The total time period from blood withdrawal to storage of plasma at approximately -20 °C should not exceed 60 minutes. The primary samples (aliquot A) should be transferred to the A&M analytical laboratory on dry ice.

6.12.2 Assay Methodology

Pharmacokinetic samples will be analyzed for the concentration of PP-001 using a validated liquid chromatography-tandem mass spectrometry method at the bioanalytical laboratory.

6.13 Total Blood Volume Collected

Patients will have approximately 20 mL of blood collected for safety and pharmacokinetic evaluations during the study.

6.14 Discontinuation from Treatment or Study

Patients are free to withdraw from the study at any time for any reason. Patients may be withdrawn from the study at the discretion of the Principal Investigator or Sub-Investigator at any time. Once a patient has been withdrawn from the study, they may not be re-entered. Patients who withdraw or who are withdrawn from the study will not be replaced. If a patient is discontinued from treatment or from the study, the reason for discontinuation will be collected in the eCRF.

If a patient is prematurely withdrawn from study drug treatment, the Investigator should make every effort to retain the patient in the study and perform all procedures scheduled for the follow-up. Any patient withdrawn from treatment due to an AE, serious AE (SAE) or clinically significant safety value will be evaluated by the Investigator, or a monitoring physician, and will be treated and/or followed up until the symptoms or values have either resolved or are assessed as stable by the Investigator.

6.14.1 Discontinuation from Study

A patient may be discontinued prematurely from the study for the following reasons:

- Withdrawal by patient (specify the reason in the eCRF)
- Lost to follow-up
- Death
- Physician decision (i.e., assessment that it is not in the patient's best interest to continue, or another reason; specify the reason in the eCRF)
- The sponsor may shut down the study at any time (specify the reason in the eCRF)

6.14.2 Individual Stopping Criteria

If an individual Patient meets one or more of the following criteria, the SDMB and Investigator will discuss whether the patient should be withdrawn from the study or dosing, or postponed until the criterion is no longer met:

- Patient develops a concurrent illness, condition or procedural complication that would interfere with the patient's continued participation
- Patient experiences a study drug-related SAE as determined by the Investigator

Patients may also be withdrawn from the study at any time at the discretion of the Investigator for other safety or tolerability reasons, or for behavioural or administrative reasons.

A patient may also withdraw from the study at any time at their own request.

If a patient is prematurely withdrawn from study treatment, the Investigator should make every effort to retain the patient in the study and to perform all procedures scheduled for the follow-up visit. Any patient withdrawn from treatment due to an AE, SAE or clinically significant abnormal laboratory test value will be evaluated by the Investigator, or a monitoring physician, and will be treated and/or followed up until the symptoms or values have either resolved or are assessed as stable by the Investigator.

6.14.3 Study Stopping Criteria

Dosing of further patients will be stopped if the following criterion is observed:

- A moderate or severe AE classified as being possibly, probably or definitively study-drug related or potential major safety concerns as identified by the Investigator after consultation with the SDMB are reported in more than 50% of patients in the same cohort.

Dosing will be stopped or the dose decreased if:

- One patient on any dosing day shows a possibly, probably or definitively study-drug-related SAE judged by the Investigator after consultation with the SDMB or other potential major safety concerns are identified by the Investigator in agreement with the SDMB.

6.14.4 Lost to Follow-up

If a patient does not report to the study site for a scheduled visit, study personnel will make four contact attempts: three telephone contact attempts and, if these are unsuccessful, a certified letter will be sent to the patient. The patient will be considered lost to follow-up if (1) upon receipt of delivery confirmation of the certified letter the patient does not contact the site or (2) the certified letter is returned as undeliverable within 7 days.

6.15 Premature Termination of the Trial

In the event of any SAE, which, in the investigator's opinion, justifies termination of the trial, dosing will be stopped and the sponsor will be informed immediately. The sponsor and

investigator reserve the right to terminate this trial should serious or severe AEs or any other safety issue occur during the trial. If the trial is terminated prematurely, the investigator will return all eCRFs to the sponsor, and the sponsor or investigator, as appropriate, will provide a written statement of the reasons for termination. The sponsor will ensure that the relevant regulatory agencies and main research ethics committees are notified.

6.16 Contraceptive measures

Female patients of childbearing potential are not allowed to participate in this study. The definition of non-childbearing potential includes the following:

- Surgically sterile (e.g., hysterectomy with or without oophorectomy; fallopian tube ligation; endometrial ablation), at least 30 days prior to signature of the Informed Consent form
- At least 3 years post-menopause (i.e., 4 years post last menstrual period), or menopause confirmed by follicle-stimulating hormone (FSH) testing.

Fertile men need to adhere to contraceptive measures in accordance with the “Recommendations related to contraception and pregnancy testing in clinical trials, September 2014” of the Clinical Trials Facilitation Group.

Male patients must ensure that one highly effective method of contraception combined with an acceptable method of contraception is used for the entire duration of the study, from first dose up to the study follow-up visit, and must refrain from fathering a child in the 3 months following the last study drug administration. Male patients must agree with their female partners prior to screening to use the above specified methods of contraception while receiving protocol-specified medication, and for 3 months after stopping the medication.

Highly effective methods of birth control are defined as those that result in a low failure (i.e., < 1 % per year) when used consistently and correctly, such as:

- combined (estrogen and progestogen containing) hormonal contraception associated with inhibition of ovulation (oral, intravaginal, transdermal)
- progestogen-only hormonal contraception associated with inhibition of ovulation (oral, injectable, implantable)
- intrauterine device
- intrauterine hormone-releasing system
- bilateral tubal occlusion
- vasectomised partner
- sexual abstinence

Acceptable birth control methods are defined as those that result in a failure rate of more than 1% per year and include:

- progestogen-only hormonal contraception, where inhibition of ovulation is not the primary mode of action
- male or female condom with or without spermicide
- cap, diaphragm or sponge with spermicide;

Periodic abstinence and withdrawal are not acceptable methods of contraception. Female partners of male patients must be informed by their male partners about the need to use one

highly effective methods of birth control combined with an acceptable method of birth control as defined above.

